15.7 Screening visit (day -28 to -14)

Subject will be identified by driving license or any other identity card. A copy of the identity card will be kept in the subject source documents.

Subjects will be asked to sign a consent form and will be screened for study eligibility according to inclusion and exclusion criteria. The daily bowel movements frequency, history of constipation, etiology of constipation and medication use (including prescription medication) will be thoroughly assessed. Subject demographic and medical information acquired from the subject or the subject's medical chart, including age, gender, previous medical history, concomitant medications, risk factors etc. will be also recorded on the eCRF.

For subjects over 50 years old a colonoscopy report should be confirmed and available during the screening visit (see incl. #5). The Bristol Stool Scale and Rome IV questionnaire (see Appendix A, B) will be completed and signed by the investigator, who is a physician to confirm the diagnosis of Chronic Idiopathic Constipation. Findings will be recorded on the eCRF.

In addition, subjects will undergo a physical examination including digital rectal examination, vital signs measurements and blood tests or blood test results from the past 3 months (providing no recently medical changes in patient illness). PAC-QOL (see Appendix D) be completed by the subject at screening visit.

The investigator will confirm their eligibility and their physical and mental suitability to participate in this study.

Eligible subjects will then be asked to refrain from taking any medication or supplement they are using to relieve their constipation during the entire study period except as allowed under the protocol (rescue treatment is allowed as per section 15.12).

Following the screening visit, subjects will enter the run-in period, in which an e-diary will be completed (on a daily basis and before bedtime) for 14 consecutive days (run-in period). During the screening visit, patient will be trained on how to complete a daily diary and on the definitions for "complete" evacuation and digital maneuver. On the day of screening, the coordinator should determine with the subject the last day of intake of constipation medication/aid and ensure that the last intake of constipation medication/aid has been taken more than 48 hours before the first diary entry.

Doc No: 280CLD		
Rev: 01	Date: 24 May 2021	
Page 50 of 103		

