During treatment period 1, Subjects will be instructed to adhere to rescue medications rules (section 15.12) and to continue filling a daily eDiary. This will include daily recordings of capsule intake, number and time of bowel movements, clinical symptoms score, AEs/change in their health condition, and medication/supplements usage, including rescue medication.

15.10 4 weeks visit (day 28 ± 2)

Four weeks after baseline visit, an on-site visit will be conducted to evaluate subject's treatment efficacy and safety.

During the visit, the following topics will be discussed to evaluate the following:

• subject's safety (including AE/ change in general health condition)

Page 53 of 103

- eDiary completion
- compliance with capsules intake
- change in concomitant medication/rescue administration
- evolution of constipation symptoms
- device accountability: at 4 weeks visit, subject must bring back to the site all remaining capsules (including spare capsule) in his/her possession and the capsules must be counted and accounted for.
- motivation of the subject, refreshing the definitions of what is "complete" evacuation and digital maneuver or any other relevant topic.

In this visit the subject will receive capsules supply for Treatment period 2 (period of 4 weeks between this visit and termination visit).

During treatment period 2, Subjects will be instructed to adhere to rescue medications rules (section 15.12) and to continue filling a daily eDiary. This will include daily recordings of capsule intake, number and time of bowel movements, clinical symptoms score, AEs/change in their health condition, and medication/supplements usage, including rescue medication

15.11 8 weeks visit / Termination (day 56 ± 2)

Eight weeks after baseline visit, an on-site visit (final visit) will be conducted to evaluate the following:

- subject's safety (including AE/ change in general health condition).
- eDiary completion
- concomitant medication/rescue administration
- evolution of constipation symptoms
- device accountability: At 8W visit, subject must bring back to the site the base unit and the router as well as all remaining capsules in his/her possession and the capsules must be counted and accounted for.
- PAC-QOL, and ease of use questionnaires

Page 54 of 103

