17.2 Study Endpoints

17.2.1 Primary Efficacy Endpoint

There are two primary efficacy endpoints for this study.

The two primary efficacy endpoints are the CSBM1 success rate, defined as an increase from the run-in period of at least one weekly Complete Spontaneous Bowel Movement (CSBM) during at least 6 of the 8 weeks of treatment, and CSBM2 success rate, defined as an increase from the run-in period of at least two weekly Complete Spontaneous Bowel Movement (CSBM) during at least 6 of the 8 weeks of treatment.

The study will be deemed successful if either the CSBM1 or the CSBM2 success rate is statistically significantly higher in the active arm, than in the placebo arm.

Doc No: 280CLD Rev: 01 Date: 24 May 2021

Page 66 of 103

17.2.2 **Secondary Efficacy Endpoints**

Secondary efficacy endpoints include:

- Change from baseline in average straining. 1.
- 2. CSBM1 expanded success rate, defined as an increase from the run-in period of at least one weekly Complete Spontaneous Bowel Movement (CSBM) during at least 5 of the 8 weeks of treatment.
- Change from baseline in average stool consistency, using the Bristol Stool Scale 3.
- 4. CSBM2 expanded success rate, defined as an increase from the run-in period of at least two weekly Complete Spontaneous Bowel Movement (CSBM) during at least 5 of the 8 weeks of treatment
- 5. Change from baseline in average bloating.

17.2.3 **Additional Efficacy Endpoints**

Additional efficacy endpoints include:

- SBM success rate, defined as an increase from baseline at least one weekly spontanuous Bowel Movement (SBM) during at lease 6 out of 8 weeks of treatment.
- Incidence of Rescue Medication use during the treatment period.
- Change from baseline in weekly number of Spontaneous Bowel Movement (SBM).
- Change from baseline in weekly number of Complete Spontaneous Bowel Movement (CSBM).
- Rate of SBM < 24 hours after first dose
- Change from baseline in average abdominal gas.
- Change from baseline in average abdominal pain.
- Change from baseline in abdominal discomfort.
- Time to occurrence of spontaneous bowel movement after first capsule activation.
- Change from baseline in quality of life using the PAC-QOL (Patient Assessment of Constipation Quality of Life) questionnaire.

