17.9 Statistical Analysis

17.9.1 General Considerations

Statistical analyses will be performed using SAS® v9.4 or higher (SAS Institute, Cary NC, USA).

Baseline demographic and other baseline characteristics, together with safety analyses will be performed on all enrolled subjects.

Baseline values are defined as the last valid value prior to treatment.

All statistical tests will be two-sided. If statistical tests are performed nominal p-values will be presented. Where confidence limits are appropriate, non-adjusted two-sided 95% confidence interval will be constructed.

For comparison of means (continuous variables), the two-sample t-test or the Wilcoxon rank sum test will be used as appropriate. For comparison of proportions (categorical variables), the Chi-squared test or Fisher's exact test will be used as appropriate.

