17.9.5 Efficacy Analysis

Doc No: 280CLD Rev: 01 Date: 24 May 2021

Page 73 of 103

The subject's CSBM1 success status (i.e. if the subjects achieve an increase from baseline of at least 1 weekly CSBM during at least 6 out of the 8 treatment weeks) will be presented in tabular form by study arm, along with 95% Wilson score Confidence Intervals (CI) and will be compared between the study arms with a Cochran-Mantel-Haenszel test controlling for center.

The CSBM2, the expanded CSBMs and the SBM success rates will be analyzed in a similar manner.

The incidence of rescue medication and the rate of SBM within 24 hours from the first study dose use will be analyzed in a similar manner.

The change from baseline in average straining will be modeled with an Analysis of Covariance (ANCOVA) model, with baseline average straining and site entered as covariates. The adjusted means of the change from baseline per study arm, and the difference between the groups will be presented along with respective 95% CI. The change from baseline in average stool consistency, in average bloating, in weekly number of SBM and CSBM, and in symptoms will be analyzed with similar ANCOVA models.

Time to occurrence of SBM after intake of the first Vibrant capsule (either active or placebo) will be assessed and presented by Kaplan-Meier curves and will be compared between the study arms using the Log-Rank test if relevant.

Treatment satisfaction, and incidence of use of rescue medication will be presented in tabular form.

The PAC-QoL, the rescue medication use, and the rate of SBM during the first 24 hours after the first dose will be presented in tabular form.

17.9.6 **Treatment by Center Interaction**

Poolability will be tested in the primary analysis at a significance level of 10%.

Poolability across centers, for the primary endpoints, will be assessed using a logistic regression model.

Centers will be grouped together by geographical area, a table of the sites and their geographical area within and without the USA will be presented. If found significant, the reason for the significance would be further explored and rationalized. This evaluation may include demographic features, symptoms at presentation, clinical and treatment history, and site comparability in the features found to be associated with the primary performance variable.

Doc No: 280CLD	
Rev: 01	Date: 24 May 2021
Page 74 of 103	

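### PAC-QOL change is a listed efficacy endpoint, but 17.9.5 names only a table for it and leaves it out of the baseline-adjusted ANCOVA used for the other change-from-baseline endpoints

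*Combined protocol and SAP*

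**What the plan says.** Section 17.2.3 includes among the additional efficacy endpoints "Change from baseline in quality of life using the PAC-QOL (Patient Assessment of Constipation Quality of Life) questionnaire"; the synopsis and 13.2 list it too. The questionnaire is to "be completed by the subject at screening visit" (15.7), and the 8-week visit again lists "PAC-QOL, and ease of use questionnaires" (15.11). Table 1 in 15.18 shows the same two time points. Section 17.9.1 defines baseline as the last valid pre-treatment value, so the screening score is the PAC-QOL baseline.

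Section 17.9.5 models change in straining by ANCOVA "with baseline average straining and site entered as covariates", reporting adjusted means and the between-arm difference with 95% CIs. It then extends this method to further endpoints: "The change from baseline in average stool consistency, in average bloating, in weekly number of SBM and CSBM, and in symptoms will be analyzed". PAC-QOL is not in that list. Its only mention in 17.9.5 is "The PAC-QoL, the rescue medication use, and the rate of SBM during the first 24 hours after the first dose will be presented" as a table.

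The general rule in 17.9.1 is: "For comparison of means (continuous variables), the two-sample t-test or the Wilcoxon rank sum test will be used as appropriate". That section also makes testing conditional, and provides unadjusted 95% confidence intervals where appropriate.

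**The concern.** PAC-QOL is the trial's only quality-of-life endpoint and the only change-from-baseline endpoint with no named model. This assumes that symptoms, in "and in symptoms will be analyzed with similar ANCOVA models", covers abdominal gas, pain and discomfort, which is the natural reading.

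Two things are at stake. First, the between-arm quality-of-life estimate is either not planned or has a method that is not fixed in advance: t-test or Wilcoxon, with the variable to be compared left open. Second, if a comparison is made under 17.9.1, it ignores a baseline score that is already collected. It would then generally be less precise, and it would not be comparable with the adjusted differences reported for the other continuous endpoints.

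**Working it through.** **1. What each additional endpoint in 17.2.3 receives in 17.9.5**

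| Endpoint | Comparative method |
|---|---|
| SBM success; rescue use; SBM within 24 hours of first dose | Analysed like CSBM1 (Cochran-Mantel-Haenszel by center) |
| Weekly SBM, weekly CSBM | ANCOVA, baseline and site |
| Abdominal gas, pain, discomfort | ANCOVA, under symptoms |
| Time to first SBM | Kaplan-Meier, log-rank if relevant |
| PAC-QOL | None named; table |

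Rescue use and SBM within 24 hours share the table sentence with PAC-QOL, but each has a comparative method earlier in the section. PAC-QOL has none.

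**2. The plan's sample size**

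The documents give no SD, correlation, effect or power for PAC-QOL. The only calculation (17.4) is for the primary endpoints: 12% vs 40%, two-sided 2.5%, 80% power. With pooled variance and a mean rate of 0.26:

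n = [2.2414 × √(2 × 0.26 × 0.74) + 0.8416 × √(0.12 × 0.88 + 0.40 × 0.60)]² / 0.28² = (1.390 + 0.495)² / 0.0784 = 45.3, so 46 per arm.

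This agrees with the stated 92, which is used below.

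**3. Baseline adjustment alone**

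Assume the same SD (σ) at screening and week 8, and correlation r.
- Change score: per-subject variance 2σ²(1 − r)
- ANCOVA: per-subject residual variance σ²(1 − r²)
- Ratio, ANCOVA to change score: (1 + r)/2
- Ratio of CI widths: √[(1 + r)/2]

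| r (assumed) | Variance ratio | CI narrower by |
|---|---|---|
| 0.3 | 0.65 | 19.4% |
| 0.5 | 0.75 | 13.4% |
| 0.7 | 0.85 | 7.8% |
| 0.8 | 0.90 | 5.1% |

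**4. Adding site, as the planned model does**

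About 30 centers (synopsis, 15.1) and 92 subjects give 92/30 ≈ 3 per center. With fixed site effects, a center contributes information a × b/(a + b), where a and b are its numbers in the two arms. A 2:1 center contributes 2/3. If all subjects were in such centers, 92/3 = 30.7 centers would contribute 30.7 × 2/3 = 20.4. Without site terms the figure is 46 × 46/92 = 23. The inflation is 23/20.4, about 1.12.

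Simulating 92 subjects over 30 centers of equal expected size, with 1:1 blocks of 2 or 4 within center and no outcome variance between centers, gives the same inflation of about 12%. Block sizes are not given in the documents.

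Residual degrees of freedom fall from 90 (two-sample) to 92 − 30 − 2 = 60. The t quantile ratio is 2.000/1.987 = 1.007. The CI width ratio is then √[1.12 × (1 + r)/2] × 1.007.

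| r (assumed) | Width ratio | CI change |
|---|---|---|
| 0.3 | √0.728 × 1.007 = 0.859 | about 14% narrower |
| 0.5 | √0.840 × 1.007 = 0.923 | about 8% narrower |
| 0.7 | √0.952 × 1.007 = 0.983 | about 2% narrower |
| 0.8 | √1.008 × 1.007 = 1.011 | about 1% wider |

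Uneven center sizes give similar figures (nil at r = 0.8 in one such calculation). With 20 centers, the narrowing at r = 0.7 is about 5%.

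**The case against.** A reader might infer that 17.9.5 rules out any PAC-QOL comparison. It does not. The section does not say that PAC-QOL is only tabulated, and the same sentence covers two endpoints that are also compared between arms. CSBM1, too, is presented as a table alongside a test. The supportable statement is narrower: no comparative method is named for PAC-QOL.

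A reader might also infer that the plan certainly loses precision, by 19%, 13% or 8% in CI width. That does not follow, for two reasons. The figures apply only if a change-score comparison is made under 17.9.1, and the plan does not commit to one. They also describe adjustment for baseline alone, whereas the planned model includes site. With about three subjects per center, site terms give back much of the gain, and at r = 0.8 all of it. If centers do differ in outcome, some gain returns, but the documents give no figure for this.

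Finally, PAC-QOL lies outside the primary endpoints and the secondary hierarchy, and describing such an endpoint without a model is a legitimate choice. That limits the importance of the point. It does not explain why this one change-from-baseline endpoint is treated differently, and the plan gives no reason. The case for naming a comparison in advance does not depend on r.

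**Conclusion.** The point stands as a minor improvement. PAC-QOL change is a declared efficacy endpoint with both scores collected, yet its only named analysis is a table, and the fallback is conditional and unadjusted. The firm part is the missing pre-specified comparison, consistent with the other continuous endpoints.

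The precision gain is secondary. Relative to an unadjusted change score, with site in the model, it is about 14%, 8% and 2% of CI width at r = 0.3, 0.5 and 0.7, and nil or slightly negative at r = 0.8. These figures assume equal SDs at the two visits, 92 subjects in about 30 centers, blocks of 2 or 4, and no outcome variance between centers. The range for r is also an assumption. No success criterion, alpha, sample size or interim rule changes.

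**What to change.** In 17.9.5, add change in PAC-QOL to the sentence that applies similar ANCOVA models, with the screening PAC-QOL score and site as covariates. Report adjusted means by arm and the between-arm difference with its 95% CI. Remove PAC-QOL from the table sentence. Keep it as an additional endpoint outside the hierarchy.

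The cost is one line of text and one more model using code already planned for the other endpoints. No further data are needed.

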17.9.7 Safety Analysis

Adverse events (AE) will be presented by seriousness, severity and relation to treatment, by treatment group. The number of reports, the number of subjects, and the incidence (percent of subjects) will be tabulated by study arm.

17.9.8 Handling of Missing Data

Subjects with less than 6 weeks of diary data will be considered as failures for the CSBM and SBM success rates, as the primary imputation method for missing data.

Additional sensitivity analysis of the primary end-point will be performed to assess the impact of missing data on the study outcome using possible imputation methods for binary data:

- Multiple imputation for binary data.
- Observed Data: Use only subjects with 8 weeks of non-missing diary data and who did not withdraw early from study.
- Best Case Scenario: Assume all subjects with missing data in study group are successes; Assume all subjects in the placebo group with missing data are failures.
- Worst Case Scenario: Assume all subjects with missing data in study group are failures; Assume all subjects in the placebo group with missing data are successes.

In addition, for missing diary day, the number of bowel movement will be imputed to "0", and the intake of rescue medicine to "No". For the time to first SBM analysis, subjects with no known SBM will be considered left censored.

For the analyses of the other endpoints, no imputations for missing values will be performed.

Doc No: 280CLD

Rev: 01 Date: 24 May 2021

Page 75 of 103

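### The 6-week diary cut-off in 17.9.8, as worded, also covers the 5-of-8-week expanded CSBM rates and fails a subject who met the endpoint in 5 recorded weeks

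*Combined protocol and SAP*

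**What the plan says.** Section 17.9.8 gives the main missing-data rule for the responder endpoints: "Subjects with less than 6 weeks of diary data will be considered as failures for the CSBM and SBM success rates". It also sets bowel movements to zero on a missing diary day. For everything else it says: "For the analyses of the other endpoints, no imputations for missing values will be performed".

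Section 17.2.1 defines the primary CSBM1 rate as an increase over run-in of "at least one weekly Complete Spontaneous Bowel Movement (CSBM) during at least 6 of the 8 weeks of treatment"; CSBM2 has the same 6-of-8 form. The SBM success rate in 17.2.3 is also a 6-of-8 endpoint.

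Section 17.2.2 lists two expanded rates with a lower week count. Expanded CSBM1 needs "at least one weekly Complete Spontaneous Bowel Movement (CSBM) during at least 5 of the 8 weeks of treatment", and expanded CSBM2 needs "at least two weekly Complete Spontaneous Bowel Movement (CSBM) during at least 5 of the 8 weeks of treatment". They are items 2 and 4 of five, and 17.9.2.3 tests the secondary endpoints in that order.

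Section 17.9.5 adds no separate missing-data rule for them: "The CSBM2, the expanded CSBMs and the SBM success rates will be analyzed in a similar manner".

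**The concern.** The cut-off in 17.9.8 matches the week count of the primary and SBM endpoints. It does not match the week count of the expanded endpoints, yet the phrase that sets its scope is general enough to include them. Where it applies, the missing-data rule gives a different answer from the endpoint definition, even though the recorded data already settle the answer: five success weeks are on file, and nothing in the other three weeks could undo them.

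The rule also ranks subjects inconsistently. Five success weeks out of six recorded is an expanded success; five out of five recorded is a failure.

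What is at stake is the second and fourth steps of the fixed secondary sequence. Non-significance at step 2 closes stool consistency, expanded CSBM2 and bloating; non-significance at step 4 closes bloating only. The sensitivity analyses in 17.9.8 are written for the primary endpoint, so none of them would reveal the effect.

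**Working it through.** **Step 1. The plan's own sample size.** Inputs from 17.4: 12% on placebo, a difference of 28 points (so 40% on active), two-sided 2.5% per endpoint, 80% power. The two-proportion formula with pooled variance and no continuity correction gives 46 per arm, 92 in total, with power 80.7%. The plan's figure reproduces. Section 17.4 raises this to 51 per arm for 10% drop-out; 51 is used below.

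**Step 2. Does the cut-off conflict with the definitions?** Each of the 8 weeks is missing, a success or a non-success, which gives 3^8 = 6,561 patterns. For each pattern, compare the definition alone with the definition plus the cut-off.

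| Endpoint | Cut-off for failure | Patterns meeting the definition but scored as failure |
|---|---|---|
| 6 of 8 weeks | fewer than 6 weeks | 0 |
| 5 of 8 weeks | fewer than 6 weeks (as worded) | 56 |
| 5 of 8 weeks | fewer than 5 weeks | 0 |

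The 56 patterns are the C(8,5) = 56 ways of having exactly 5 recorded weeks, all 5 successful. No other pattern is affected: a subject with 6 or more recorded weeks and 5 successes remains an expanded success.

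**Step 3. How many subjects have exactly 5 weeks?** The documents do not say. Assume that the planned 10% drop-out is spread evenly over 8 weeks and that no diary weeks are lost otherwise:

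- 51 per arm: 51 × 0.10 / 8 = 0.64 subjects.
- 125 per arm (the cap of 250 in 17.5.3): 125 × 0.10 / 8 = 1.56 subjects.

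**Step 4. How many are re-scored?** Only those who respond in all 5 weeks. The documents give no such probability. The 12% and 40% of 17.4 are borrowed as an assumed range:

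- 51 per arm: 0.64 × 0.12 = 0.08, and 0.64 × 0.40 = 0.26 subjects.
- 125 per arm: 1.56 × 0.12 = 0.19, and 1.56 × 0.40 = 0.62 subjects.
- Change in the between-arm difference at 51 per arm: 0.64 × 0.28 / 51 = 0.0035, about 0.35 percentage points.

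**Step 5. Less favourable assumptions.** If weeks are lost independently, the share with exactly 5 is 56 × (1 − q)^5 × q^3. The loss rates q are illustrations, not document figures.

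| Weekly loss q | Share with exactly 5 weeks | Per 51 | Re-scored at 12% to 40% |
|---|---|---|---|
| 5% | 0.5% | 0.28 | 0.03 to 0.11 |
| 10% | 3.3% | 1.69 | 0.20 to 0.68 |
| 15% | 8.4% | 4.28 | 0.51 to 1.71 |

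A wider grid, with 1% to 10% of subjects having exactly 5 weeks and 12% to 60% of those responding throughout, runs from 51 × 0.01 × 0.12 = 0.06 to 51 × 0.10 × 0.60 = 3.06 subjects per arm. One subject is 1/51, or about 2.0 percentage points.

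**Step 6. Power.** Suppose, for illustration, that the expanded rates were also 12% and 40%, tested at 2.5% with 51 per arm. Power is 85.0% without the rule and 83.9% if 2% of responders in each arm are lost to it. The even-drop-out case loses 10%/8 = 1.25%, so it costs less than that.

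**The case against.** **Scope.** 17.9.8 never names the expanded rates, whereas 17.9.5 lists them separately from CSBM2 and SBM. One could read the cut-off as meant for the three 6-of-8 rates only, which it fits exactly. This stands as an ambiguity but does not remove the problem. The ordinary meaning of the CSBM success rates includes the expanded ones. If they are instead among the other endpoints, no imputation applies, and the plan does not say how an incomplete diary is scored for them. Either reading needs a sentence.

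**A deliberate completeness requirement.** A minimum-data rule stricter than the response count is permissible if prespecified; it applies equally to both arms and can only remove responders. But the plan states no such intention. Unrecorded weeks need no further safeguard, since missing days already count as zero bowel movements. And it is not a rule that drop-outs fail: someone who leaves after 6 successful weeks remains a primary success.

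**Size.** This part of the objection stands in full. A reader might take 0.64 or 1.56 per arm, or 0.5%, 3.3% and 8.4%, as the number re-scored. Those figures count everyone with exactly 5 weeks; the number re-scored is smaller. The random-loss rates also have no basis in the documents, which describe a daily diary alert (15.7) and coordinator monitoring of the diary during run-in (15.8).

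**Conclusion.** The mismatch is real on the ordinary reading of the text and is confined to one case: exactly 5 recorded weeks, all successful. Under the plan's own drop-out rate, spread evenly, the expected effect is about 0.08 to 0.26 subjects per 51-subject arm, well below one. It exceeds one subject only under assumptions such as 15% weekly loss, or 5% or more of subjects with exactly 5 weeks combined with high response among them. The sample size of 92 is unaffected.

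Three stronger conclusions might be inferred and are not supported. First, that the rule would produce a wrong result and stop the sequence: no calculation shows a changed test outcome, and the effect is at most a small loss of power. Second, that type I error is inflated: the rule only removes responders, applies to both arms alike, and no inflation is shown. Third, that the cut-off was copied from the primary endpoints by mistake: the fit suggests it, but no section gives its origin.

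The point is worth correcting because the affected endpoints are in the confirmatory sequence, no planned sensitivity analysis would expose the effect, and the correction is cheap. The counts assume whole weeks. Section 17.9.8 does not define a week of diary data, and the 5-day standard in 17.8.3 is tied to mITT evaluability only, so partly completed weeks could enlarge the affected group.

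**What to change.** Replace the first rule in 17.9.8 with two cut-offs. Fewer than 6 diary weeks is a failure for the CSBM1, CSBM2 and SBM success rates. Fewer than 5 diary weeks is a failure for the expanded CSBM1 and expanded CSBM2 success rates. State that unrecorded weeks count as non-success, and give one definition of a diary week that serves both cut-offs.

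The cost is one or two sentences and no new data. Make the change before any unblinded look, so that it cannot appear data-driven.

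There is a small downside. A subject who leaves after 5 successful weeks, for whatever reason, will count as an expanded responder. That matches how the plan already treats a subject who leaves after 6 successful weeks on the primary endpoints. If the sponsor does want the stricter requirement for the expanded rates, 17.9.8 should name them and say so.
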